## 192 **Secondary outcomes**

193 The secondary outcomes include functional scales (physical, role, emotional, cognitive, and social)  
194 and symptom scales (fatigue, nausea and vomiting, pain, dyspnea, insomnia, appetite loss,  
195 constipation, diarrhea, and financial difficulties) from the EORTC QLQ-C30 questionnaire).

196 In addition to the EORTC QLQ-C30 scales, leisure-time exercise will be included as a secondary  
197 outcome and will be assessed using the GSLTPAQ, including the frequency and duration of mild,  
198 moderate and strenuous exercise.

199 [Time frame for each participant: Baseline + end point at 16 weeks + follow up at 3 months and 12  
200 months]

201 Continued participation in any high intensity functional training (post-intervention HIFT) will be  
202 assessed using a single-item modified version of the (GSLTPAQ) asking participants: *During a*  
203 *typical 7-Day period (a week), how many times on the average do you do High Intensity Functional*  
204 *Training (I.E. CrossFit) for more than 15 minutes during your free time.* The participant responds  
205 by typing how many times per week, starting from zero.

206 [Time frame: for each participant at follow up at 3 month and 12 months]

207

208

## 209 **Participation timeline**

210 The inclusion of participants will be consecutive as patients are referred to CCHC for physical  
211 cancer rehabilitation from various hospitals in the Capital Region in Denmark (see figure 1 for  
212 participation flow of each participant).

213 Self-reported baseline data will be collected using online questionnaires sent out to patients via  
214 email within four days prior to beginning the supervised HIFT intervention. After completing the 16  
215 weeks of high intensity functional training the patient will receive an end point questionnaire.

216 Three months following completing the exercise intervention, participants will be contacted via  
217 email to complete a follow-up questionnaire also including questions regarding continued  
218 participation in HIFT. All participants will receive an identical follow-up questionnaire 12 month

219 after completing the intervention.

220

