### 133 Intervention

134 The exercise intervention for this study will be HIFT, as defined by Feito et al and described in the  
135 introduction of this study protocol (13). The program design and template will be based on the  
136 principles of the HIFT program called CrossFit®. CrossFit is described as a strength and  
137 conditioning program that focuses on “constantly varying functional movements, performed at a  
138 relatively high intensity” (23). CrossFit training includes a variety of elements from gymnastics  
139 (e.g., floor, bar and ring exercises), weightlifting exercises (e.g., squats, cleans, snatches and presses  
140 with a barbell, dumbbell or kettlebell), and cardiovascular activities (e.g., running or rowing) (24).

141  
142 All group training sessions will take place in a clinical setting at CCHC.

143 The full exercise protocol template is designed as a 38-week HIFT program, as the inclusion of  
144 participants will be consecutive. All participants will complete 16 weeks of twice weekly group-  
145 based HIFT sessions, under the supervision of two physiotherapists, specifically trained to deliver  
146 the HIFT program. Given the consecutive nature of this inclusion process, the participants will  
147 initiate the group-based training at different dates between august 5th 2019 and January 5th 2019 (see  
148 figure 2 for process of HIFT program implementation and figure 3 for timeline of the study period  
149 with important dates).

150

151 Each training session will last for one hour and 15 minutes and will include a general warmup, a  
152 strength-focused section including 1-3 exercises and a aerobic-focused workout.

153 The exercise program is not developed to include a general progression in terms of resistance,  
154 intensity or volume over the cause of 38 weeks. An exercise compendium will be developed to meet  
155 one of the key principles of CrossFit, that is scalability (25). The compendium will include  
156 movement standards as well as progressions and regressions of all included exercises. This is to  
157 assist the supervising physiotherapists in choosing the relevant level of intensity and exercise  
158 difficulty for each participant, and to allow for individual progression over the cause of the 16-week  
159 exercise intervention period for each participant.

160

161 **Patient-reported outcomes**

162 **EORTC:**

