## 239 **Methods: Data collection, management and analysis**

### 240 **Data collection methods**

#### 241 **Plan for assessment and collection of outcomes**

242 All primary and secondary outcomes are participant-reported and will be administered through the  
243 online survey tool: SurveyXact. All included participants will receive an email with an electronic  
244 SurveyXact\_invitation to the baseline questionnaire the same days as providing written consent to  
245 participate in the study. On the day of the final HIFT session (week 16), the participants will receive  
246 a similar SurveyXact\_invitation with the end-point questionnaire. The three and 12-month follow up  
247 assessments will be administered in identical ways to the end-point assessment.

248

249 **Patient characteristics**

250 Demographic variables will be included in the baseline questionnaire. These will include self-  
251 reported information about: sex, body mass index, educational level, employment, smoking status  
252 and physical activity level, and will be collected together with information on cancer type, time  
253 since cancer diagnosis, time since active treatment and cancer treatment type.

254

255 **Registration of adverse events, plans to promote participant retention and complete follow  
256 up:**

257 Adverse events and reasons for drop out from discontinued participant will be collected by  
258 practising physiotherapists at CCHC.

259 To minimize non-response and loss to follow-up participants will receive a reminder by email 4 and  
260 14 days after receiving the email with end-point and follow-up questionnaire if they haven't  
261 provided their responses.

262

263 **Data management**

264 All outcomes will be handled and stored electronically on a secure server for personal data, located  
265 at the University of Copenhagen.

266 No personal data will be exported from SurveyXact without pseudonymization. Complete  
267 anonymization of all data will be done after the last follow up period. Data protection agency  
268 approval Reference number: 514-0306/19-3000

269

270 **Statistical methods**

271 Descriptive statistics will be used to summarize patient characteristics including age, sex, cancer  
272 diagnosis and type of treatment. Furthermore, leisure-time HIFT exercise and HRQoL at baseline  
273 will be summarized using the GSLTPAQ LSI score and the EORTC QLQ-C30 GH score  

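### Questionnaire send rules are tied to completing training; no visible text says early stoppers are sent the forms or what date anchors their follow-ups

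*Combined protocol and SAP*

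**What the plan says.** **Send rules.** Participation timeline sends the end-point form once the training is done: after the 16 "weeks of high intensity functional training the patient will receive an end point questionnaire". The next form is dated the same way: "Three months following completing the exercise intervention, participants will be contacted via" email. The last one goes to everybody, but is again counted from completion: "All participants will receive an identical follow-up questionnaire 12 month" after the intervention ends. Plan for assessment and collection of outcomes places the end-point invitation at the last session (the quoted run opens with the tail of the preceding sentence): "participate in the study. On the day of the final HIFT session (week 16), the participants will receive" the survey link. It adds that the follow-ups are administered in the same way.

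**Who is meant to be assessed.** Primary outcomes and Secondary outcomes set baseline, 16 weeks, 3 months and 12 months as the time frame for each participant. Sample size says that all participants will be asked for the baseline, end-point and three-month assessments.

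**Completion and drop-out.** Intervention takes completion as given: "All participants will complete 16 weeks of twice weekly group"-based sessions. The paragraph on adverse events and retention does not: "Adverse events and reasons for drop out from discontinued participant will be collected by" the physiotherapists. Its reminders run from the arrival of a form, at 4 and "14 days after receiving the email with end-point and follow-up questionnaire if they" have not answered.

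**The concern.** A send rule worded around completion works for completers. For them the two sections agree with each other and with the 16-week time frame. It does not tell staff what to do for a participant who stops training in, say, week 4. That person has a nominal 16-week end point, but no instruction that the form goes out then and no completion date from which to count 3 and 12 months. The reminders cannot close the gap, because they start only after a form has been received.

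If staff follow the wording and send nothing, the later scores do not exist. The baseline to end-point comparison (paired t-test or Wilcoxon) needs both scores, and the four-time-point analysis needs the later ones, so both would rest mainly on completers. Objective makes feasibility the primary aim and change in quality of life a secondary, descriptive one, but Primary outcomes lists quality of life as the primary outcome. Scores that were never requested cannot be recovered afterwards. How many stop, and how many of those still reply, is also useful feasibility information.

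**Working it through.** **1. The plan's own figure.** Sample size expects about 30 participants from 6 starters a month over 22 weeks. At 365.25/12/7 = 4.348 weeks per month, 6 × 22/4.348 = 30.4; over five calendar months, 6 × 5 = 30. The figure reproduces. It is an accrual projection, and the plan gives no drop-out rate, SD or expected change.

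**2. Send dates for someone who stops at week 4** (an assumed example; 3 months = 13.0 weeks, 12 months = 52.2 weeks). Weeks are counted from the first session.

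| Reading | End point | 3-month form | 12-month form |
|---|---|---|---|
| Completer | 16 | 29 | 68 |
| Stopper: rule applies to completers only | not sent | not sent | not sent |
| Stopper: dated from last session attended | 4 | 17 | 56 |
| Stopper: dated from scheduled week 16 | 16 | 29 | 68 |

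The last row fits the stated time frames best, but no visible sentence selects it. The last two rows differ by 16 - 4 = 12 weeks at every form, so the choice also decides whether one time level in the analysis means one time.

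**3. How many could be affected.** With assumed stopping of 10%, 20%, 30% or 40%, that is 3, 6, 9 or 12 of 30, leaving 27, 24, 21 or 18 with later scores if stoppers are sent nothing.

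**4. Possible effect on the reported change.** Every input is an assumption: completers change by c = 8 points; a share p stops; stoppers change by d; a share r of stoppers replies if sent a form, and repliers are typical of stoppers.

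- Change in all enrolled: (1 - p)c + pd
- Reported change with no stopper scores: c
- Reported change with a share r replying: [(1 - p)c + prd] / [(1 - p) + pr]

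With p = 0.25 (7.5 of 30) and d = -5:

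- All enrolled: 0.75 × 8 + 0.25 × (-5) = 4.75, so the gap is 8 - 4.75 = 3.25.
- r = 0.5: (6 - 0.625)/0.875 = 6.14. Sending the forms removes 1.86 points and leaves 1.39.
- r = 0.3: 5.625/0.825 = 6.82; removes 1.18, leaves 2.07.
- r = 0.8: 5/0.95 = 5.26; removes 2.74, leaves 0.51.

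Over p = 0.15 to 0.35, d = -10 to +12 and r = 0.3 to 0.8, the extremes of the removable part are:

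- p = 0.35, d = -10, r = 0.8: (5.2 - 2.8)/0.93 = 2.58; removes 5.42 of a gap of 6.3.
- p = 0.35, d = +12, r = 0.8: (5.2 + 3.36)/0.93 = 9.20; removes -1.20 of a gap of -1.4, so here the completer figure was too low.
- d = 8: zero, whatever p and r.

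**5. Scale.** With an assumed SD of change of 20, the 95% confidence half-width at n = 30 is t(0.975, 29) × 20/√30 = 2.045 × 3.651 = 7.47 points.

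**The case against.** The strongest reply is that the plan already intends to assess everyone and that the wording around completion only describes the planned schedule. Each participant has a 16-week end point, all are to be asked, all are to get the 12-month form, and the last session is itself labelled week 16. This stands as far as it goes. A reader might infer that early stoppers have no end-point time at all, or that the plan confines its analysis to completers. The documents support neither: the outcome sections state a nominal time for each participant, and Statistical methods contains no completer restriction. What remains is that no operative rule delivers the form to a stopper, and that the 3- and 12-month dates hang on a completion that never happens for that person.

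Two further points have weight. Drop-out may mean leaving the study, in which case no form is due; the text does not say which is meant, and a rule limited to those who still accept contact covers both meanings. The participant flow (Figure 1), the timeline (Figure 3) and the participant information are not visible and may settle the matter. If they do, the two sections that govern sending should repeat the rule.

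Finally, the illustration is not evidence of bias. Its inputs are all assumed, the effect may be zero or reversed, and in the central example it is smaller than sampling error. That limits the weight of the point without removing it, since this kind of selection would not shrink with more participants.

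**Conclusion.** The point holds as a gap between intent and procedure. The intended assessment times cover everyone; the send rules cover completers. Taken literally, the rules would leave the analyses of the listed primary outcome describing mainly people who finished. A reader might go further and conclude that the reported improvement will be inflated. The documents do not support that, because they give no drop-out rate and no information on how stoppers fare. On the assumptions shown, the part that sending the forms could correct runs from 5.4 to -1.2 points and includes zero, against a half-width of about 7.5.

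In an exploratory single-group study of about 30, this is a clarification that should be made because it is cheap and the missing scores cannot be recovered. It does not undermine the design. Confidence is medium, mainly because the figures and the participant information could not be read.

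**What to change.** **Sending (Participation timeline; Plan for assessment and collection of outcomes).** Leave the completers' trigger as it is. Add that participants who stop training early, and have not withdrawn consent to contact, are sent the end-point form at their scheduled week 16, meaning 16 weeks from their first session. Send them the follow-ups 3 and 12 months after that date, with the same reminders.

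**Analysis (Statistical methods).** State that the planned tests include everyone with the required scores, whether or not they finished training. Report how many stopped and how many of them replied at each time point. Optionally, add a mixed model on all available scores as a supporting analysis; the send rule does not depend on it.

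**Cost.** Record each first-session date, set one scheduling rule in the existing survey tool, and add a few sentences.

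**Downsides.** Some stoppers will not reply, so any bias is reduced rather than removed. Their follow-ups come later after the actual last session than for completers: for a stop at week 4, the 3-month form at week 29 is 29 - 4 = 25 weeks afterwards, against 13 for a completer. This matters when reading the question on continued HIFT. The reported change may also be smaller.

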## 221 **Sample size**

222 Due to the exploratory nature of this study, no power calculation will be conducted. As the  
223 inclusion of participants will be consecutive, the anticipated number of included participants will be  
224 estimated based on the average monthly number of patients that begins the group based training  
225 during clinical practise at the centre. The average number of patients who is referred to the  
226 rehabilitation centre and who begins the HIFT training every month is 6 and thus, it is expected that  
227 a total of approximately 30 participants will be included in this study during a 22-week consecutive  
228 inclusion period that runs from august 5th 2019 to January 5th. All participants will be asked to  
229 complete both baseline-, end point- and three-month follow-up assessment.

230

## 231 **Recruitment**

232 Due to the pragmatic design there will be no recruitment through advertisement. Recruitment will  
233 take place by asking eligible patients referred to CCHC, if they would like to participate in the  
234 study. This recruitment will take place during an initial rehabilitation planning session with a  
235 physiotherapist two days prior to the first HIFT session. Patients will be made aware that they have  
236 two days to consider participating in the study (written participant information can be found in  
237 [appendix 1](#)).

238

## 239 **Methods: Data collection, management and analysis**

### 240 **Data collection methods**

#### 241 **Plan for assessment and collection of outcomes**

242 All primary and secondary outcomes are participant-reported and will be administered through the  
243 online survey tool: SurveyXact. All included participants will receive an email with an electronic  
244 SurveyXact\_invitation to the baseline questionnaire the same days as providing written consent to  
245 participate in the study. On the day of the final HIFT session (week 16), the participants will receive  
246 a similar SurveyXact\_invitation with the end-point questionnaire. The three and 12-month follow up  
247 assessments will be administered in identical ways to the end-point assessment.

248

249 **Patient characteristics**

250 Demographic variables will be included in the baseline questionnaire. These will include self-  
251 reported information about: sex, body mass index, educational level, employment, smoking status  
252 and physical activity level, and will be collected together with information on cancer type, time  
253 since cancer diagnosis, time since active treatment and cancer treatment type.

254

255 **Registration of adverse events, plans to promote participant retention and complete follow  
256 up:**

257 Adverse events and reasons for drop out from discontinued participant will be collected by  
258 practising physiotherapists at CCHC.

259 To minimize non-response and loss to follow-up participants will receive a reminder by email 4 and  
260 14 days after receiving the email with end-point and follow-up questionnaire if they haven't  
261 provided their responses.

262

263 **Data management**

264 All outcomes will be handled and stored electronically on a secure server for personal data, located  
265 at the University of Copenhagen.

266 No personal data will be exported from SurveyXact without pseudonymization. Complete  
267 anonymization of all data will be done after the last follow up period. Data protection agency  
268 approval Reference number: 514-0306/19-3000

269

270 **Statistical methods**

271 Descriptive statistics will be used to summarize patient characteristics including age, sex, cancer  
272 diagnosis and type of treatment. Furthermore, leisure-time HIFT exercise and HRQoL at baseline  
273 will be summarized using the GSLTPAQ LSI score and the EORTC QLQ-C30 GH score  
274 respectively. Quantile Quantile plots and histograms will be used to evaluate distribution of  
275 standardized residuals. Continuous data with normally distributed standardized residuals will be  
276 summarized using parametric statistics. Continuous data with without normally distributed  
277 standardized residuals will be summarized as ordinal data, using non-parametric statistics.  
278 Categorical data will be summarized using frequencies and % of total.

279 The EORTC QLQ outcomes will be conducted according to the EORTC QLQ-C30 scoring manual  
280 (ref fayes 2001). Numerical data for each outcome with normal distributed standardized residuals,  
281 will be analysed from baseline to end-point with parametric statistics (paired t-test with equal  
282 variance). Single-Factor Repeated Measures Design will be conducted with a repeated measures  
283 one-way analysis of variance with four within subject time levels: baseline, end-point, three month  
284 follow up, and 12-month follow up. Summary statistics will include mean and confidence intervals  
285 for each outcome.

286 Numerical data for each outcome, without normal distributed standardized residuals, or ordinal data  
287 will be analyzed from baseline to end-point with non-parametric statistics (Wilcoxon signed-ranks  
288 test). Single-Factor Repeated Measures Design will be conducted with a Friedman two-way  
289 analysis of variance by ranks with four within subject time levels: baseline, end-point, three months  
290 follow up, and 12-month follow up. Summary statistics will include medians and interquartile  
291 ranges for each outcome, and visualizations will include bar charts with confidence intervals.

292 The association between leisure-time HIFT exercise and HRQoL will be analyzed on each time  
293 point with a linear regression model. To test whether the associations varies, the coefficients from  
294 the linear regression analyses will be compared.

295 Stata 15.1 (StataCorp, College Station, TX, USA) will be used for all statistical analyses and  
296 illustrations and an alpha level of 0.05 or less will be considered statistically significant.

297

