## 95 **Objective**

96 The primary objective of this pragmatic clinical trial is to test the feasibility of the intervention in a  
97 real world setting and secondary, to describe whether the HRQoL of the participants changes from  
98 baseline to end-point and follow up time points. Furthermore, we will investigate the association  
99 between the leisure-time HIFT and the HRQoL.

100

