163 EORTC QLQ-C-30 includes five functional domains (physical, role, cognitive, emotional and  
164 social, where higher scores represent greater function or quality of life) and three symptom scales  
165 (fatigue, pain and nausea). Functional and symptom scales range from 0 to 100. Higher values on  
166 functional scales equal a higher level of functioning. Higher values on symptom scales equal higher  
167 symptom burden. EORTC QLQ-C-30 is chosen for its established reliability and validity with  
168 specific emphasis on use in cancer populations (26, 27).

169 **GLTEQ:**

170 Leisure time physical activity (LTPA) will be assessed using an original Danish translation of the  
171 Godin-Shephard Leisure-Time Physical Activity Questionnaire (GSLTPAQ). The GSLTPAQ is  
172 frequently used in oncology research to assess LTPA.

173 The GSLTPAQ is a 4-item self-administered questionnaire. The first three questions ask for  
174 information on the number of times the respondent engages in mild, moderate and strenuous LTPA  
175 bouts of at least 15 min duration in a typical week. A score is then calculated for total leisure time  
176 based on the numerical values attributed to each of the three categories (9 for strenuous, 5 for  
177 moderate and 3 for light) multiplied by the frequency of the activity. The scores derived from this  
178 method is called a Leisure Score Index (LSI). In addition, scores obtained from moderate and  
179 strenuous physical activity can be used to classify respondents into active and insufficiently active  
180 categories.

181 A recently published systematic review by Amireault et al, supports the use of the GSLTPAQ in  
182 oncology research and the interpretation of the LSI for assessing relative change in PA among  
183 cancer survivors.

184

185 **Primary outcomes**

186 HRQoL will be evaluated using the Global Health Status/Quality of Life item from the EORTC  
187 QLQ-C-30 questionnaire. The item ranges from 0 to 100, and higher values equal higher HRQoL.

188 Time frame: for each participant at baseline + end point at 16 weeks + follow up at 3 month and 12  
189 months)

190

191

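### HRQoL change from baseline has no planned estimate with a confidence interval at any visit, and at 3 and 12 months the omnibus test is the only comparison over time

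*Combined protocol and SAP*

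**What the plan says.** The Objective section puts feasibility first ("The primary objective of this pragmatic clinical trial is to test the feasibility of the intervention in a" real-world setting). Second, it asks whether HRQoL changes from "baseline to end-point and follow up time points". Primary outcomes then names the global QLQ-C30 score, measured at four visits: "Time frame: for each participant at baseline + end point at 16 weeks + follow up at 3 month and 12" months.

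Statistical methods has two paths, chosen from residual plots.

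- Parametric: each outcome "will be analysed from baseline to end-point with parametric statistics (paired t-test with equal" variance), followed by a repeated-measures "one-way analysis of variance with four within subject time levels: baseline, end-point, three month" and 12 months. The summaries are described as "follow up, and 12-month follow up. Summary statistics will include mean and confidence intervals" for each outcome.
- Non-parametric: each outcome "will be analyzed from baseline to end-point with non-parametric statistics (Wilcoxon signed-ranks" test), followed by the omnibus analysis ("test). Single-Factor Repeated Measures Design will be conducted with a Friedman two-way" analysis by ranks) over the same four visits. The summaries are medians and interquartile ranges, with intervals on bar charts.

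Neither path names a contrast, a post-hoc comparison or a change score for 3 or 12 months. The data collection section expects non-response: it plans reminders at 4 and 14 days and has reasons for drop-out recorded. No section says how a wholly missed questionnaire enters the analysis.

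**The concern.** The HRQoL question covers three changes: baseline to week 16, to 3 months and to 12 months. The analysis compares only the first directly. For the other two, a reader of the results would have an omnibus p-value and summaries of scores. The p-value says that some visits differ, but not which ones or by how much. The summaries, read as one per visit, would show the shape of the means but not the uncertainty of a change, which depends on the within-person correlation.

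At stake is whether the study can say, by plan, if a gain at the end of training is kept a year later, and how precisely. Contrasts that are not written down would be chosen after the data are seen. The silence on missed questionnaires adds to this, because the two paths could analyse different people: a Friedman test needs all four scores, while an ANOVA may or may not, depending on how the data are laid out.

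**Working it through.** **Inputs from the documents.** About 30 participants, at 6 a month over 22 weeks (Sample size). Check: 22 x 7 / 30.44 = 5.06 months, and 6 x 5.06 = 30.4, so the figure reproduces. The four visits fall at about weeks 0, 16, 29 and 68, because follow-up runs 3 and 12 months from the end of the 16 weeks. Alpha is 0.05. The documents give no SD, correlation or non-response rate.

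**Assumptions.** SD 20 points at each visit; correlation exchangeable at 0.5 or 0.7, or decaying at 0.8 per 16 weeks; 20,000 simulated trials per cell with complete data; ANOVA with Greenhouse-Geisser correction (the plan names none).

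**1. What the omnibus test can distinguish.** Under exchangeable correlation its power depends on the visit means only through the sum of their squared deviations from their own average.

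- Fading gain (0, +10, +5, 0): average 3.75; sum 14.06 + 39.06 + 1.56 + 14.06 = 68.75.
- Lasting gain (0, +10, +10, +10): average 7.5; sum 56.25 + 3 x 6.25 = 75.
- Gain at week 16 only (0, +10, 0, 0): average 2.5; sum 56.25 + 3 x 6.25 = 75.

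The last two are identical to the test, and the first is close. Simulated rejection rates, with correlation in the order 0.5 / 0.7 / decaying:

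| | Fading | Lasting |
|---|---|---|
| ANOVA | 74 / 93 / 85% | 78 / 95 / 85% |
| Friedman | 62 / 86 / 88% | 66 / 88 / 85% |
| Paired 12-month 95% interval excludes 0 | 5 / 5 / 5% | 76 / 92 / 67% |

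Repeat simulations agree to about one point.

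**2. Per-visit intervals do not give the interval for a change.** With n = 30:

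- one visit: 2.045 x 20 / sqrt(30) = 7.5 points either side;
- change: 2.045 x 20 x sqrt(2(1 - r)) / sqrt(30) = 7.5 at r = 0.5 and 5.8 at r = 0.7;
- change rebuilt as if the visits were independent: 2.00 x 20 x sqrt(2/30) = 10.3.

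The rebuilt interval is 1.4 to 1.8 times too wide (10.3/7.5 and 10.3/5.8).

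**3. Missed questionnaires.** Assume 10%, 20% and 30% missing at week 16, 3 months and 12 months. Pairs with baseline are 27, 24 and 21. Complete sets of four are 30 x 0.9 x 0.8 x 0.7 = 15 if misses are independent, or 30 x 0.7 = 21 if those who stop do not return.

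**4. Precision of the proposed estimate.** The half-width is t(n-1) x SD of change / sqrt(n). With an SD of change of 20 it is 7.9, 8.4 and 9.1 points for 27, 24 and 21 pairs.

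**5. Choice of method for the change.** At n = 30 with complete data and correlation decaying at 0.7, 0.8 or 0.9 per 16 weeks, the 12-month 95% interval from a compound-symmetry (random-intercept) model covers the truth in only 86-89% of trials. It over-covers at week 16 (about 99%). The paired interval covers about 95%.

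**6. Bias from non-response.** Assume a true 12-month change of +5, 70% complete, and odds of staying that change by 1.5 to 4.5 times per SD of score. If the previous score drives loss, complete pairs give +2.1 to +4.7 and an unstructured likelihood model gives +5.0 to +5.1; the +2.1 needs the strongest dependence and the fastest decay. If the unseen current score drives loss, complete pairs give +5.2 to +6.5 and the model +5.7 to +8.6. Neither method is safe in both cases.

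**The case against.** The strongest defence is that the study is exploratory, has no power calculation, puts feasibility first and asks only to describe HRQoL. The omnibus test includes baseline, the summaries will show the pattern of means, and follow-up contrasts are routine after such a test. Reminders and recorded reasons for drop-out show that non-response was considered. Most of this stands as a limit on weight. It does not close the gap: a descriptive aim needs estimates with intervals more than it needs p-values, no contrast is written, and reminders prevent loss without saying how to analyse it.

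A reader might infer more than the documents support.

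- That the follow-up scores go unanalysed. They enter the omnibus test, and also the regressions on leisure-time HIFT, although those do not estimate change.
- That anyone with one missed questionnaire is necessarily lost. This is certain for Friedman and for an ANOVA on complete sets, but an ANOVA on long-format data keeps incomplete participants. The planned paired week-16 test is untouched by later misses.
- That the HRQoL results will be biased in a known direction. The documents say nothing about who will stop responding, and the direction differs between plausible mechanisms.
- That a mixed model must replace the planned analysis. Paired changes on available pairs answer the question with a standard error only 1-7% larger than the unstructured model's in simulation, and the model's advantage on bias depends on an assumed mechanism.
- That the switch on residual plots must go. Nothing in this point requires it.

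The description of the summaries as per visit is itself a reading: the text says for each outcome and mentions neither visit nor change. On that wording week 16 has no explicit interval for change either.

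**Conclusion.** The point holds. Followed exactly, the plan gives no baseline contrast at two of the three visits that its own HRQoL question covers, no change with an interval at any visit, and no rule for missed questionnaires. The planned omnibus test separates a lasting from a fading gain by 4 percentage points at most (ANOVA or Friedman); the paired 12-month interval separates them by 62 points or more (5% against 67-92%). These figures rest on assumed SD, correlations, effect patterns and complete data. The count of 15 to 21 complete sets rests on assumed non-response. That an omnibus test does not locate or size a change needs no assumption. The consequence is limited to how far the HRQoL objective can be interpreted; the feasibility objective is unaffected. It should be changed because the remedy is cheap, not because the study fails without it.

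**What to change.** In Statistical methods, for global HRQoL, the other QLQ-C30 scales and the GSLTPAQ score:

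- Report change from baseline with a 95% confidence interval at week 16, 3 months and 12 months, using everyone with both scores at that visit. Give the mean change with a paired-t interval; where the plan's non-parametric path applies, give the Wilcoxon signed-rank test with the median change and its interval.
- Report the number responding at each visit.
- Keep the ANOVA or Friedman test as a supporting analysis, and leave the residual-plot rule as it is.
- Label results for the secondary scales exploratory and unadjusted for multiplicity.

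For global HRQoL, add two sensitivity analyses. First, a linear mixed model on all observed scores, with visit as a four-level factor and unstructured covariance; if it does not converge, rely on the paired changes and do not fall back on compound symmetry. Second, an analysis in which missing follow-up scores are assumed worse, for example by 10 points. With 20% and 30% missing this lowers the 3- and 12-month means by 0.2 x 10 = 2.0 and 0.3 x 10 = 3.0 points.

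The single item on continued HIFT is asked only at 3 and 12 months, so it has no change from baseline and stays descriptive.

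Cost: plan wording and a few lines in the Stata already specified, with no new data or visits. There are more intervals to report: 15 QLQ-C30 scales plus the GSLTPAQ score make 16 outcomes, and 16 x 3 = 48 changes. Available-pairs estimates can be biased if earlier scores drive non-response, and the mixed model can be biased if the unseen score does, which is why both are shown.
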